11.2 Assessment of Intensity

Each AE will be classified according to the following criteria:

Mild:	The AE does not interfere in a significant manner with the participant's normal level of functioning.
Moderate:	The AE produces some impairment of functioning but is not hazardous to the participant's health.
Severe:	The AE produces significant impairment of functioning or incapacitation and is a definite hazard to the participant's health.

Severity versus Seriousness: Severity is used to describe the intensity of a specific event while the event itself, however, may be of relatively minor medical significance (such as severe headache). This is not the same as "seriousness," which is based on participant/event outcome at the time of the event.

When changes in the intensity of an AE occur more frequently than once a day, the maximum intensity for the experience should be noted. If the intensity category changes over several days, those changes should be recorded separately (with distinct onset dates).

11.3 Assessment of Causality

Each AE will be assessed as to its relationship to the IMP, based on the following criteria. Although the attribution by the investigator will be collected for reported events, for analytic purposes a temporal association with the use of the IMP will be assumed sufficient for at least

plausible association. All noxious and unintended responses to the IMP related to the dose should be reported as Adverse Drug Reactions (ADR).

Not related:	No causal relationship exists between the IMP and the AE, but an obvious alternative cause exists, eg the participant's underlying medical condition or concomitant therapy.
Possibly related:	A connection with the administration of the IMP appears unlikely but cannot be ruled out with certainty. An AE may be considered possibly related if or when it meets 2 of the following criteria: (1) it follows a reasonable temporal sequence from administration of the IMP; (2) it could not readily have been produced by the participant's clinical state, environmental or toxic factors, or other modes of therapy administered to the participant; or (3) it follows a known pattern of response to the IMP.
Related:	There is a reasonable/plausible possibility that the AE may have been caused by the IMP.

When assessing the relationship to the IMP, the following criteria will be considered:

- Known class effect
- Biological plausibility
- Lack of alternative explanation—concomitant drug or disease

11.4 Action Taken Regarding Investigational Medicinal Product

Dose modifications of IMP (eg dose not changed, drug withdrawn, drug interrupted, or dose increased) are not applicable as this is a single dose study.

- Not Applicable: Participant died, study treatment had been completed prior to reaction/event, or reaction/event occurred prior to start of treatment

11.5 Other Action Taken for Event

Other possible actions that can be taken for event are the following:

- None (eg no treatment was required)
- Medication required (eg prescription and/or OTC medication was required to treat the AE)
- Hospitalisation or prolongation of hospitalisation required (eg hospitalisation was required or prolonged because of the AE, whether medication was required)
- Other

11.6 Adverse Event Outcome

The outcome of AEs can be defined as one of the following:

- Recovered/Resolved (eg the participant fully recovered from the AE with no residual effect observed)
- Recovering/Resolving (eg the AE improved but has not fully resolved)
- Not Recovered/Not Resolved (eg the AE itself is still present and observable)
- Recovered/Resolved with Sequelae (eg the residual effects of the AE are still present and observable, including sequelae/residual effects)
- Fatal (eg ‘fatal’ should be used when death is a direct outcome of the AE)
- Unknown

11.7 Clinical Laboratory Changes

Clinically significant abnormalities in a laboratory value that is new in onset or which has worsened in severity or frequency from the baseline condition and meets one of the following criteria will be recorded and reported as an AE:

- Requires therapeutic intervention or diagnostic tests
- Has accompanying or inducing symptoms or signs
- Is judged by the investigator as clinically significant

Combined elevations of aminotransferases and bilirubin, either serious or nonserious, and whether causally related, meeting the criteria of a potential Hy’s Law case (total bilirubin level $\geq 3 \times$ upper limit of normal [ULN] with simultaneous ALT or AST $\geq 3 \times$ ULN) should always be reported to the sponsor as soon as possible following the procedures outlined in [Section 10.2](#) for SAE reporting, with the investigator’s assessment of seriousness, causality, and a detailed narrative.

11.8 Overdose

Any instance of overdose (suspected or confirmed) must be communicated to the CRO, within 24 hours and be fully documented as an AE or SAE if it meets the SAE criteria. Details of any signs or symptoms and their management should be recorded including details of any antidote(s) administered.

11.9 Adverse Events of Special Interest

An adverse event of special interest (AESI) is an AE (serious or nonserious) of scientific and medical concern specific to the study drug, for which ongoing monitoring and immediate

notification by the investigator to COMPASS and the CRO is required. Such AEs may require further investigation to characterise and understand them.

The following events will be reported as AESI:

AESI term	MedDRA Preferred Terms
• Euphoric mood	• Euphoric mood
• Dissociative disorder	• Dissociative disorder; Dissociative identity disorder; Dissociative amnesia; Dissociation; Depersonalisation/derealisation disorder
• Hallucination	• Hallucination; Hallucination, auditory; Hallucination, synaesthetic; Hallucination, tactile; Hallucination, visual; Hallucination, olfactory; Hallucinations, mixed; Somatic hallucination
• Psychotic disorder	• Psychotic disorder; Psychotic behaviour; Acute psychosis; Hysterical psychosis; Reactive psychosis; Substance-induced psychotic disorder; Brief psychotic disorder with marked stressors; Brief psychotic disorder without marked stressors; Transient psychosis
• Cognitive disorder	• Cognitive disorder
• Disturbance in attention	• Disturbance in attention
• Mood altered	• Mood altered; Depressed mood; Affect lability; Fluctuating mood symptoms
• Psychomotor skills impaired	• Psychomotor skills impaired
• Inappropriate affect	• Inappropriate affect
• Overdose	• Overdose
• Intentional product misuse	• Intentional product misuse

The investigator must report to COMPASS and the CRO all the above events within 24 hours of learning about the event regardless of relationship to study drug.

The report should include the following minimum information:

- Participant number
- Event
- Date/time of onset
- Duration of the event
- Dose of drug taken
- Severity
- Outcome

11.10 Adverse Event Follow-up

All SAEs related to the IMP will be followed until resolved or stable and the outcome documented. All AESIs will be followed up until the end of the study.

If the investigator detects an AE in a study participant after the last scheduled follow-up visit and considers the event possibly related or related to prior study treatment, the investigator should report it to COMPASS and the CRO.

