Clinical laboratory evaluations will be performed including blood chemistry, haematology, urinalysis, urine drug screen, and urine pregnancy test (for women of childbearing potential). Blood samples for clinical laboratory tests will be collected at screening, baseline, and day 2. Urine samples will be collected at screening and baseline. The details of the analyses are listed in Table 8.1. and in the Schedule of Assessments in Section 5.3.

Table 8.1 List of clinical laboratory evaluations

Haematology	Chemistry
Haemoglobin	Albumin
Haematocrit	Alkaline phosphatase
Red blood cell count	Alanine aminotransferase (ALT)
Mean corpuscular haemoglobin	Amylase
Mean corpuscular volume	Aspartate aminotransferase (AST)
Mean corpuscular haemoglobin concentration	Bicarbonate
White blood cell count (with differential)	Bilirubin (direct, indirect, and total)
Platelet count	Calcium
	Chloride
	Creatine kinase
	Creatinine
	Gamma-glutamyl transferase
	Glucose
	Lactate dehydrogenase
	Lipase
	Magnesium
	Phosphate
	Potassium
	Protein-total
	Sodium
	Urea (blood urea nitrogen)
	Uric acid
Urinalysis (dipstick)	Urine Drug screen
Blood	Amphetamines
Glucose	Barbiturates
Ketone	Benzodiazepines
Protein	Cocaine
pH	Cannabinoids
Specific gravity	Opiates
Nitrite	
Leukocytes	
Bilirubin	
Urobilinogen	
Others	
Urine pregnancy dipstick	

8.2.5 *Adverse Events*

All AEs occurring after the participant signs the ICF and up to the last study event will be recorded. Any AEs occurring before the start of treatment (eg, before the dose of the IMP on day 1) will be recorded as pre-treatment AEs. Any SAE ongoing at V12 (EOS/ET) will be followed until resolution or no longer considered clinically significant.

See [Sections 11](#) and [12](#) for additional information.

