12.2 Definition of Terms

Life-threatening: An AE is life-threatening if the participant was at immediate risk of death from the event as it occurred; eg it does not include a reaction that if it had occurred in a more serious form might have caused death. For example, drug-induced hepatitis that resolved without evidence of hepatic failure would not be considered life-threatening even though drug-induced hepatitis can be fatal.

Hospitalisation: AEs requiring hospitalisation should be considered SAEs. Hospitalisation for elective surgery or routine clinical procedures that are not the result of AEs (eg elective surgery for a pre-existing condition that has not worsened) need not be considered AEs or SAEs. If anything untoward is reported during the procedure, that occurrence must be reported as an AE, either 'serious' or 'nonserious' according to the usual criteria.

In general, hospitalisation signifies that the participant has been detained (usually involving at least one an overnight stay) at the hospital or emergency ward for observation and/or treatment that would not have been appropriate in the physician's office or outpatient setting. When in doubt as to whether 'hospitalisation' occurred or was necessary, the AE should be considered serious.

For deaths, the underlying or immediate cause of death should always be reported as an SAE.

Any serious, untoward event that may occur subsequent to the reporting period that the investigator assesses as related to IMP should also be reported and managed as an SAE.

The investigator should follow participants with AEs until the event has resolved or the condition has stabilised. In case of unresolved AEs, including significant abnormal clinical laboratory values at the end of study assessment, these events will be followed until resolution or until they become clinically not relevant.

Disability/incapacitating: An AE is incapacitating or disabling if the experience results in a substantial and/or permanent disruption of the participant's ability to carry out normal life functions.

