All SAEs shall be followed until resolution, until the condition stabilises, or until the participant is lost to follow-up, or otherwise explained. Once the SAE is resolved, the corresponding AE eCRF page shall be updated. Additionally, any relevant laboratory test reports, consultation reports from other health care professionals, discharge summaries, or other information that has been gathered about the event shall be transmitted to the sponsor.

In the case of a “minimum report” (one that solely comprises the information bulleted above), a more detailed follow-up report should be sent as soon as more information becomes available but no later than 7 calendar days after the date of the initial report. Each SAE should be followed up until resolution or stabilisation and for reported deaths, the investigator should supply the CRO and the IRB/IEC with any additional requested information (eg, autopsy reports and terminal medical reports).

The original SAE form should be kept at the study site. The sponsor or its representative will be responsible for determining and in turn, reporting SAEs to regulatory authorities according to the applicable regulatory requirements.

All SAEs will be followed until resolved or stable and the outcome documented on the eCRF.

Investigator safety reports will be prepared for suspected unexpected serious adverse reactions (those not listed in the IB) according to local regulatory requirements and COMPASS/the CRO policy and are forwarded to investigators as necessary.

An investigator who receives an investigator safety report describing an SAE(s) or other specific safety information (eg summary or listing of SAEs) from COMPASS or the CRO will file it with the IB and will notify the IRB/IEC, if appropriate according to local requirements.

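### Protocol 11.10 sets narrower follow-up for non-serious AESIs and unrelated SAEs than 8.2.5, 12.2 and 12.3, and the SAP's top duration class pools resolved long events with events still open at the last visit

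*Protocol*

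**What the plan says.** Four protocol sections set follow-up rules for events that have not resolved.

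- Section 11.10, on AESIs: "All AESIs will be followed up until the end of the study". On SAEs: "All SAEs related to the IMP will be followed until resolved or stable and the outcome documented".
- Section 12.2, on AEs in general: "The investigator should follow participants with AEs until the event has resolved or the condition has stabilised". For the end of the study it continues: "In case of unresolved AEs, including significant abnormal clinical laboratory values at the end of study assessment", and then "these events will be followed until resolution or until they become clinically not relevant".
- Section 12.3, on SAEs: "All SAEs shall be followed until resolution, until the condition stabilises, or until the participant is lost to follow-up, or otherwise explained".
- Section 8.2.5: "Any SAE ongoing at V12 (EOS/ET) will be followed until resolution or no longer considered clinically significant".

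Section 11.9 defines an AESI as an AE, serious or not. Section 7.2.10 makes Visit 10, at 12 weeks ± 7 days, both the End of Study visit and the early-termination visit. The protocol does not define the end of the study for the purpose of 11.10.

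SAP 8.3.1 puts TEAEs, TESAEs and AESIs into duration classes. The last class takes events longer than 7 days together with events still ongoing. SAP 10.1 applies the classes in Tables 14.3.1.6, 14.3.1.8 and 14.3.1.10, and treats AEs whose end date is genuinely missing as ongoing.

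**The concern.** AEs are part of the primary endpoint (Protocol 3.1), and AESIs are the events that the protocol singles out as being of concern for this drug. Where two sections give different stopping points for the same event, sites may apply different rules. Whether an event's final outcome and end date are known then depends on which section the site read, not on the event.

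Two groups are exposed: non-serious AESIs still present at the last visit, and SAEs judged unrelated.

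The SAP adds a reporting problem. An event closed by the calendar has a cut-off duration, and its row in the duration tables also holds events that lasted more than a week and resolved. A reader of the tables cannot tell a persistent effect from one that was simply recent when observation stopped.

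**Working it through.** The plan gives no figure to reproduce, so the check is a comparison of the rules, some calendar arithmetic, and a look at how the SAP class handles typical events.

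**1. The rules side by side**

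| Section | Events covered | Follow-up ends when |
|---|---|---|
| 8.2.5 | any SAE ongoing at EOS/ET | resolved, or no longer clinically significant |
| 11.10 | SAEs related to the IMP | resolved or stable |
| 11.10 | all AESIs | end of the study |
| 12.2, general sentence | AEs | resolved or stabilised |
| 12.2, end of study | AEs unresolved at that assessment | resolved, or clinically not relevant |
| 12.3 | all SAEs | resolved, stabilised, lost to follow-up, or otherwise explained |

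**2. Applying them by event class**

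- *Non-serious AESI, ongoing at Visit 10.* It is an AE, so 12.2 applies and sets no calendar limit. Section 11.10 also applies and names only the end of the study. The stopping points differ.
- *Serious AESI.* 8.2.5 and 12.3 apply whatever 11.10 says about AESIs, so these events are covered past the last visit.
- *SAE judged unrelated.* 8.2.5 and 12.3 require follow-up. The SAE sentence in 11.10 does not reach it.
- *SAE judged related.* All the SAE rules apply, with slightly different end conditions.

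No section of the protocol or SAP states an order of precedence for these rules.

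**3. Calendar limit if 11.10 is applied alone**

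Assume that the end of the study means the participant's own Visit 10.

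- Visit 10 falls at 12 × 7 ± 7 = 84 ± 7, that is 77 to 91 days after dosing, or earlier at early termination.
- An AESI starting d days after dosing is observed for at most 91 − d days.
- The Week 9 contact falls at 63 ± 3, that is day 60 to 66. For onset at that contact, the time to the nominal Visit 10 is 84 − 66 = 18 to 84 − 60 = 24 days. To the latest Visit 10 it is 91 − 66 = 25 to 91 − 60 = 31 days.
- For an AESI first reported at the EOS or ET visit, further observation is zero.

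**4. What the SAP class pools**

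Three illustrative events, using the date formula in SAP 15.5 (stop − start + 1), with Visit 10 at day 84 after dosing:

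- onset on the day of dosing, resolved 8 days later: 8 − 0 + 1 = 9 days, resolved;
- onset on the day of dosing, still present at Visit 10: 84 − 0 + 1 = 85 days observed, ongoing;
- onset on day 80, still present at Visit 10: 84 − 80 + 1 = 5 days observed, ongoing.

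All three land in the same row, although the third has been observed for less than 7 days.

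**5. Visit label**

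Section 8.2.5 attaches its rule to V12. The schedule of assessments ends at Visit 10, which falls at Week 12, so V12 is a slip for V10.

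**6. Size per participant**

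With the maximum of 20 participants treated, one affected participant is 1/20 = 5% of the Safety Analysis Set.

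**The case against.** The strongest reply is that the rules can be obeyed together. Section 11.10 does not say that follow-up stops. It can be read as a minimum, so that every AESI is followed to the end of the study even if stable, with 12.2 taking over for those unresolved. Likewise a site that follows 12.3 satisfies the SAE sentence in 11.10. This is a fair reading, but the text does not state it, and a site that consults only the section titled for AE follow-up would not find it.

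Several stronger inferences are not supported:

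- *That AESIs get the shortest follow-up of any event.* The general sentence in 12.2 allows an ordinary AE to be closed once stabilised, whereas 11.10 keeps a stabilised AESI under follow-up to the end of the study. AESI follow-up can therefore be the longer of the two.
- *That all AESIs are exposed.* Serious ones fall under 8.2.5 and 12.3.
- *That 12.2 demands resolution.* It also accepts events that are no longer clinically relevant.
- *That exposed events have no outcome.* Section 11.6 provides a category for events not recovered. What may be missing is the final outcome and end date.
- *That the SAP cannot separate an 8-day event from one present at Week 12.* SAP 10.1 lists every AE with its dates, duration and outcome, and AESIs have their own listing (16.2.7.3). Only the summary tables pool them.

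It can also be said that late or persistent events will be few. In the completed healthy-volunteer trial cited in Protocol 1.2.2, 343 of 403 TEAEs starting on the dosing day resolved that day. That is useful context, but it concerns a different population and leaves 403 − 343 = 60 that did not.

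**Conclusion.** The point holds in a limited form. Section 11.10 is narrower than 12.2 for non-serious AESIs and narrower than 8.2.5 and 12.3 for unrelated SAEs, and no precedence is given. The consequence is conditional: it arises where a site relies on 11.10 alone and, for AESIs closed at Visit 10, reads the end of the study as the participant's own last visit. The documents give no basis for estimating how often that would happen. The 5% is the weight of one participant in a set of 20, not an expected rate.

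The pooling in the SAP duration tables is certain by construction whenever an event is open at the last visit, but the listings limit its effect.

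Two matters of version and timing bear on this. The SAP is written to protocol V5.0, and the supplied protocol appears to differ from it: for example, it names the Measure Health app where the SAP names the Cue app, and it has no BPRS+. Whether V5.0 keeps the follow-up wording should be checked. The SAP addendum was made after database lock, so changes to protocol wording may no longer alter conduct in this trial.

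This is worth correcting because it concerns the primary safety endpoint and costs little. It is not evidence that the safety data are unsound.

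**What to change.** **Protocol.** Reconcile 8.2.5, 11.10, 12.2 and 12.3 into one follow-up rule, and have the other sections refer to it. Set it out by event class (AE, AESI, related SAE, unrelated SAE) and by exit route (end of study, early termination), and say what the end of the study means. How long each class is followed is for the sponsor to decide. Correct V12 to V10 in 8.2.5. Confirm first that V5.0 still carries this wording.

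**SAP.** In 8.3.1 and Tables 14.3.1.6, 14.3.1.8 and 14.3.1.10, replace the pooled top class with two: more than 7 days and resolved, and ongoing at last contact. Footnote any events counted as ongoing only because the end date is missing.

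**If the database is already locked.** Make the table split, and state in the clinical study report which follow-up rule was applied to AESIs and SAEs open at the last visit.

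**Cost.** Protocol wording, one extra row in each of three tables, and occasional contact with a few participants after Week 12, which 12.2 and 12.3 already imply.

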12 SERIOUS ADVERSE EVENTS

12.1 Definition of Serious Adverse Event

An SAE is any event that meets any of the following criteria:

- Death
- Life-threatening
- Inpatient hospitalisation or prolongation of existing hospitalisation
- Persistent or significant disability/incapacity
- Congenital anomaly/birth defect in the offspring of a participant who received psilocybin.
- Other: Important medical events that may not result in death, be life-threatening, or require hospitalisation, may be considered an SAE when, based upon appropriate medical judgment, they may jeopardise the participant and may require medical or surgical intervention to prevent one of the outcomes listed in this definition. Examples of such events are:
 - Intensive treatment in an emergency room or at home for allergic bronchospasm
 - Blood dyscrasias or convulsions that do not result in inpatient hospitalisation
 - Development of drug dependency or drug abuse

12.2 Definition of Terms

Life-threatening: An AE is life-threatening if the participant was at immediate risk of death from the event as it occurred; eg it does not include a reaction that if it had occurred in a more serious form might have caused death. For example, drug-induced hepatitis that resolved without evidence of hepatic failure would not be considered life-threatening even though drug-induced hepatitis can be fatal.

Hospitalisation: AEs requiring hospitalisation should be considered SAEs. Hospitalisation for elective surgery or routine clinical procedures that are not the result of AEs (eg elective surgery for a pre-existing condition that has not worsened) need not be considered AEs or SAEs. If anything untoward is reported during the procedure, that occurrence must be reported as an AE, either 'serious' or 'nonserious' according to the usual criteria.

In general, hospitalisation signifies that the participant has been detained (usually involving at least one an overnight stay) at the hospital or emergency ward for observation and/or treatment that would not have been appropriate in the physician's office or outpatient setting. When in doubt as to whether 'hospitalisation' occurred or was necessary, the AE should be considered serious.

For deaths, the underlying or immediate cause of death should always be reported as an SAE.

Any serious, untoward event that may occur subsequent to the reporting period that the investigator assesses as related to IMP should also be reported and managed as an SAE.

The investigator should follow participants with AEs until the event has resolved or the condition has stabilised. In case of unresolved AEs, including significant abnormal clinical laboratory values at the end of study assessment, these events will be followed until resolution or until they become clinically not relevant.

Disability/incapacitating: An AE is incapacitating or disabling if the experience results in a substantial and/or permanent disruption of the participant's ability to carry out normal life functions.

